# Fluid Management:

All subjects will receive a maintenance infusion of 125 mL lactated Ringers (LR) solution throughout the study period as per Labor and Delivery protocol. All subjects will have a bolus IV bag attached to the mainline IV per Unit protocol.

For patients in Groups A or B, an intravenous bolus of 1000 mL LR will be initiated when the patient is positioned for CSE placement by the L & D nurse. The bolus will be administered through a free-flowing wide open intravenous catheter until complete.

Patients in Groups C and D will not receive any additional fluid bolus and will only receive the maintenance infusion of 125 mL LR during the study period. Blinding will be maintained by the Labor and Delivery nurse by covering up the LR bolus fluid bag.

# Oxytocin Management:

The Prentice Women's Hospital AMOL and oxytocin protocols will be used. At the time of request for analgesia, if the patient is in group A or C, the oxytocin management will continue as per the normal oxytocin or AMOL protocol.

If the patient is randomized to groups B or D, the dose of oxytocin currently being administered will be halved and not increased for the duration of the study period (60 minutes after the initiation of CSE). Care providers other than the Labor & Delivery nurse managing the fluid and oxytocin infusions, will be blinded to group assignment.

### Analgesia Management:

Labor analgesia will be initiated in the sitting position at the L3-4 or L2-3 interspace with a routine combined spinal-epidural (CSE) technique. The epidural space will be located with the loss of resistance technique and a 27-g x 5-in pencil point spinal needle will be passed through the epidural needle to the subarachnoid space. The intrathecal injection will consist of bupivicaine 2.5 mg and fentanyl 15 μg. A 20 gauge epidural catheter will be threaded and secured 4-5 cm in the epidural space. A test dose of 3 mL lidocaine 1.5% with epinephrine 1:200,000 will be administered through the epidural catheter. The epidural catheter will be secured and the patient will be positioned in a lateral recumbent position. Patient-controlled epidural analgesia (PCEA) infusion of bupivicaine 0.0625% with fentanyl 1.95 μg/mL will be started at a rate of 15 mL/r with bolus dose = 5 mL, lock-out interval = 10 min and maximum volume = 30 mL/h.

### Fetal heart rate monitoring:

Fetal heart rate monitoring and frequency of uterine contractions will be recorded by external tocodynamometry.

# Treatment of hypotension:

Any decrease of 10% or greater from baseline in maternal systolic blood pressure after placement of the CSE will be treated by the IV administration of ephedrine or phenylephrine as guided by maternal heart rate, as per standard practice.

# Treatment of non-reassuring fetal heart rate changes:

If there are prolonged fetal heart rate decelerations, recurrent late decelerations, severe variable decelerations, or tachysystole, the Prentice Women's Hospital protocol for oxytocin management will be followed.

# Study completion:

The study is complete after 60 min after the intrathecal injection. After this time, obstetric and anesthesia management, including fluid and oxytocin management, will not be dictated by study protocol.

# Fetal heart rate tracing assessment:

Fetal heart rate tracings will be examined for 30 minutes before and 60 minutes after the initiation of analgesia by a perinatologist blinded to study group off-line after delivery. NICHD guidelines (12) will be used to assess FHR patterns. Non-reassuring FHR patterns will be defined as any one or more of the following: minimal or absent variability, late decelerations, and persistent deceleration (see Appendix).

.2.4 Risks/Benefits: All of the techniques and medications used in this study are routinely used for CSE analgesia during labor and for management of labor. The risks of the CSE procedure itself are unchanged by participating in this study. These risks include: epidural analgesia may not be effective, the epidural procedure may need to be repeated, pruritus, nausea, vomiting, or hypotension. Less common risks include maternal postdural puncture headache. Rare complications include maternal or fetal respiratory depression, total spinal anesthesia, a toxic reaction to the anesthetic agents, and bleeding or infection in

the epidural or spinal space that may lead to nerve damage. The risk of oxytocin administration includes nausea, vomiting, confusion, allergic reaction, uterine hyperstimulation, fetal bradycardia, or maternal cardiac arrhythmias. There are

no direct benefits to the patient for participating in the study.

4.0 Data Analysis:

.1 Data collection form: The following data will be collected:

Demographic data: age, race, height, weight, gravidity, parity, and gestational age.

history of prior inductions.

Labor data: time of rupture of membranes, cervical examination prior to placement of CSE (dilation, effacement, and station); start and stop time of fluid bolus, time of intrathecal injection, oxytocin dose at time of placement of CSE, vasopressor use and dose, maximum oxytocin dose in 60 minutes following placement of CSE, number of times oxytocin infusion is stopped or decreased for hyperstimulation or nonreassuring fetal status, time to complete cervical dilation, time of delivery, maximal

maternal body temperature in study period.

Mode of delivery: normal spontaneous vaginal, instrumental vaginal, Cesarean.

Neonatal data: 1- and 5-minute Appar scores; fetal umbilical cord gases (if taken);

birth weight; neonatal sepsis workup or ICU admission.

Fetal heart rate tracing data: see appendix

.2 Data evaluation:

The primary endpoint is the incidence of non-reassuring fetal heart rate tracings during the first 60 minutes after the placement of CSE. Cross tabulation tables will be

constructed with the presence or absence of the endpoint as rows and the groups as

06/07/07 V 1.1

10 of 11

columns. Differences in the frequency among groups will be assessed using a X statistic. Exact tests will be computed using Monte-Carlo sampling of 10,000 samples

with a confidence level of 99%.

Secondary outcomes and demographics: Age, height, weight, gestational age, fetal

station, and frequency of contractions will be compared using ANOVA or Kruskal

Wallis ANOVA with post-hoc comparisons correction for multiple comparisons.

Binominal and ordinal data will be compared between groups using the X statistic or

the Fisher's exact test. A P < 0.05 will be required to reject the null hypothesis.

5.0 Interpretation of Anticipated Results:

We anticipate that the combination of fluid administration and lower doses of oxytocin

will cause fewer adverse fetal heart rate changes in the first 60 minutes following

initiation of labor analgesia.

6.0 Budget:

.1 Materials: No additional materials will be required as all of the materials used in

the study are routinely used in the management of patients.

.2 Labor Requirements: Existing anesthesia personnel on Labor & Delivery Unit.

.3 Presentation Cost: Anticipated presentations at MARC, SOAP and ASA meetings.

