Proposed Research Protocol Form Northwestern University Feinberg School of Medicine

Department of Anesthesiology Research Committee

Title: The association between fluid administration, oxytocin administration, and fetal

heart rate changes.

Principal Investigator: [name]

Co-investigator (s): [name]; [name]; [name], Pharm D.

Affiliation: Department of Anesthesiology, Department of Obstetrics and Gynecology, Section

of Maternal Fetal Medicine; Northwestern University Feinberg School of Medicine

Institution: NMH

1.0 Research Aims:

.1 Research Questions(s): 1. Is there an association between the amount of intravenous

fluid administered prior to the initiation of combined spinal-epidural (CSE) analgesia

and post-analgesia fetal heart rate (FHR) non-reassuring fetal heart rate patterns? 2. Is

there an association between the rate of oxytocin administration and non-reassuring

FHR changes after the initiation of combined spinal-epidural (CSE) analgesia?

.2 Hypotheses: Patients who receive a 1000 mL fluid bolus and lower rates of

oxytocin administration will have fewer non-reassuring FHR changes.

2.0 Research significance:

Background:

Combined spinal-epidural (CSE) analgesia is a well-accepted technique for labor

analgesia. The incidence of fetal heart rate changes after the initiation of neuraxial

analgesia has been reported between 3-23% (1,2) and it is controversial whether the risk

is increased with a CSE technique compared to an epidural analgesia technique. This

06/07/07

1 of 11

wide range in reported risk may be due to fluid and oxytocin management prior to and during the initiation of neuraxial analgesia.

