#### .2 Methods:

- fetal heart rate tracings after the placement of CSE. Group sample sizes of 88 in each of the four groups achieves 80% power to detect a difference among the groups assuming an effect size (W) of 0.1900 using a 3 degrees of freedom Chi-Square Test with a significance level (alpha) of 0.05. The incidence of fetal heart rate changes was estimated based on data from Kinsella, et al (10). The proportion of subjects with adverse fetal heart rate changes in the low-oxytocin and fluid bolus treatment group is estimated to be 8%, and the proportion in the low-oxytocin, no-fluid bolus control group is estimated to be 23%. The proportion in the high-oxytocin groups is assumed to be 15% and 25% with and without a fluid bolus respectively. Therefore 380 patients will be enrolled to account for patient drop-out or ineligibility.
- .2.2 Subject entry, exclusion and dropout criteria: Healthy nulliparous or multiparous women with a term (>36 week gestation), singleton pregnancy in spontaneous labor or with spontaneous rupture of membranes, who request neuraxial analgesia, and will be managed by the active management of labor protocol (AMOL) and receive oxytocin, or receive oxytocin augmentation per PWH's protocols, will be eligible to participate in the study. Maternal exclusion criteria will include the presence of any systemic disease (e.g., diabetes mellitus, hypertension, preeclampsia); use of chronic analgesic medications; prior administration of systemic opioid labor analgesia; non-vertex presentation; scheduled induction of labor; or any contraindication to neuraxial analgesia.

2.3 Protocol specific methods: Eligible women will be asked to participate shortly after admission to the Labor & Delivery Unit at Prentice Women's Hospital during the routine pre-anesthetic interview. Informed, written consent will be obtained. Block randomization based on parity, via a computer generated random number table, will be performed and group assignments will be concealed in sealed, opaque envelopes. At the time of request for labor analgesia, group assignment will be determined by opening an opaque envelope. Patients will be randomized to one of four groups:

Group Assignment	Fluid Administration	Oxytocin Regimen
A	1000 mL bolus	Routine oxytocin
В	1000 mL bolus	Half-dose oxytocin
С	No bolus	Routine oxytocin
D	No bolus	Half-dose oxytocin

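### The tracing read in the 30 minutes before CSE is not used in the primary test; stratifying on it would be a cheap gain in precision

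*Combined protocol and SAP*

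**What the plan says.** Under *Fetal heart rate tracing assessment* in section 3.0, the reading covers both periods: "Fetal heart rate tracings will be examined for 30 minutes before and 60 minutes after the initiation of analgesia". The reader is a perinatologist blinded to group, working off-line after delivery. The same paragraph gives the event definition: "Non-reassuring FHR patterns will be defined as any one or more of the following: minimal or absent variability, late decelerations, and persistent deceleration". It refers to an Appendix, as does the data collection list in section 4.0 .1 ("Fetal heart rate tracing data: see appendix"). The Appendix is not in the supplied text.

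Section 4.0 .2 defines the outcome on the later period only: "The primary endpoint is the incidence of non-reassuring fetal heart rate tracings during the first 60 minutes after the placement of CSE". Presence or absence is cross-tabulated by group. "Differences in the frequency among groups will be assessed using a" chi-square statistic, with exact tests from 10,000 Monte-Carlo samples. No baseline term, stratum or change rule appears.

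The exclusion list in section 3.0 .2.2 begins "Maternal exclusion criteria will include the presence of any systemic disease" and does not name a non-reassuring tracing, so women who have one before CSE can be enrolled.

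Timing matters for the remedy. The envelope is opened when the woman requests analgesia (section 3.0 .2.3). The oxytocin change apparently takes place then (*Oxytocin Management*). The fluid bolus starts at positioning for CSE (*Fluid Management*).

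**The concern.** A tracing that is already non-reassuring before treatment may well predict a non-reassuring tracing afterwards. If so, part of the outcome variation can be removed by comparing groups within baseline strata. The plan pays for the reading and then leaves it out of the primary comparison. What is at stake is power, not validity.

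A smaller question concerns wording. Taken literally, the definition and the endpoint count any listed pattern seen in the 60 minutes after CSE, whatever came before. Research question 2 speaks of non-reassuring "FHR changes after the initiation of combined spinal-epidural (CSE) analgesia", and the hypotheses and sample-size paragraph also use the language of change, which could suggest new onset only. The size of the gain depends partly on which is meant.

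**Working it through.** **Inputs from the documents.** 88 women per group, 352 in all; 3 df; alpha 0.05; planned event rates (section 3.0 .2) of A 15%, B 8%, C 25% and D 23%.

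**The plan's own figure.** Mean rate = (15 + 8 + 25 + 23)/4 = 17.75%. W = sqrt[mean of (p_i - 0.1775)² / (0.1775 × 0.8225)] = 0.1769. Noncentrality = 352 × 0.1769² = 11.0, which on 3 df gives 80.4% power. The planned 80% therefore reproduces from the four rates. The printed W of 0.1900 gives 352 × 0.19² = 12.7 and 86.2% power; that mismatch is a separate matter. Direct simulation of the chi-square test at these rates gives 83.4%, slightly above the approximation. This is the reference below.

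**Assumed inputs, not in the documents.** q = share with a non-reassuring tracing at baseline (5, 10, 15%). r = probability of an event in those women (persistence).

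**Method.** 40,000 simulated trials per cell (Monte-Carlo standard error about 0.2 point). Pearson 3-df chi-square is compared with generalised Cochran-Mantel-Haenszel (CMH). In stratum s, with N_s women, t_s events and m_sj women in group j, the expected count is m_sj·t_s/N_s. Observed minus expected counts and their hypergeometric covariances are summed over strata, and the quadratic form is referred to chi-square on 3 df.

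**If a pre-existing pattern counts as an event**, four scenarios were run:
- (a) planned rates are new-onset risks, with no treatment effect in baseline-abnormal women;
- (b) as (a), but the planned odds ratios also act in those women;
- (c) planned rates are totals, with no effect in baseline-abnormal women;
- (d) planned rates are totals, with common odds ratios in both strata.

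Power in %, unadjusted → stratified, at q = 5/10/15%:

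| r | (a) | (b) | (c), unadjusted 83.2-83.8 | (d), unadjusted 83.1-83.7 |
|---|---|---|---|---|
| 30% | 77.2/70.6/63.1 → 77.5/71.1/63.7 | 84.4/85.2/86.4 → 84.2/85.2/86.6 | → 83.7/84.3/84.4 | → 83.1/83.8/83.8 |
| 50% | 75.0/65.8/57.4 → 77.0/69.3/61.3 | 84.0/85.1/86.0 → 85.0/86.9/88.7 | → 85.6/88.0/90.2 | → 84.6/86.4/88.5 |
| 70% | 72.6/62.8/53.3 → 77.4/70.6/63.3 | 81.4/79.9/79.4 → 84.9/86.0/87.8 | → 88.4/94.2/impossible | → 87.3/92.3/96.2 |

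Gains:
- r of 30% or less: -0.3 to +1.2 points.
- r = 50%: 1.0 to 4.8 points. The cell (c), q = 15% gains 6.9 but needs a group B new-onset risk of (0.08 - 0.15 × 0.50)/0.85 = 0.6%, which is implausible.
- r = 70%: 3.5 to 10.0 points. Two cells exceed this (10.8 and 13.0) but need group B new-onset risks of 1.1% and 2.0%.
- r = 90%: 8 to 20 points. Several cells under (c) and (d) have no solution.

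**If only new-onset patterns count** (planned rates are new-onset risks, no events in baseline-abnormal women, all women kept in the denominator): 80.5 → 80.9, 77.8 → 78.7 and 74.5 → 76.0 at q = 5/10/15%. The gains are 0.4, 0.9 and 1.5 points; a repeat run gave 0.5, 0.8 and 1.6.

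**If baseline is uninformative**, the loss is at most about 0.3 point. Under the null, both tests reject in 4.7-5.1% of trials.

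**The case against.** The strongest reply is that the planned test is correct as it stands and that the gain rests on two parameters the documents do not inform. That is true. At low persistence, or under a new-onset rule, the gain is slight, and the largest figures need very high persistence. The case for stratifying is that the reading is already planned and the downside is close to zero.

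Three stronger readings are tempting and are not supported.

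- *The endpoint is undefined.* The literal wording already gives an answer: any listed pattern in the 60 minutes counts. The definition also points to an Appendix that was not supplied, and the sample-size paragraph begins mid-sentence in the supplied text. Either gap may hold a rule.
- *The trial is underpowered because of pre-existing patterns.* Power falls below plan only if the planned rates are new-onset risks, and much of that fall comes from assuming no treatment effect in baseline-abnormal women. Stratifying does not recover that part.
- *Carried-over patterns could outnumber real events.* One might set 88 × 15% × 90% = 11.9 women per group against 88 × 8% = 7.0 events in group B. These figures belong to different readings. If 8% is a total, 11.9 carried-over events cannot occur. If 8% is a new-onset risk, group B expects 88 × (0.85 × 0.08 + 0.15 × 0.90) = 17.9 events.

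Two practical objections stand in part. Randomisation is blocked on parity, and crossing three tracing strata with parity would give six thin strata; the proposal here stratifies on the tracing alone. The documents also do not say that a tracing is always running before the request for analgesia, so some women may lack a usable baseline.

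**Conclusion.** The point holds as a suggestion worth considering. The plan collects a baseline reading of its own primary outcome and does not use it in the primary test. That test remains valid and unbiased.

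At prevalence of 5-15%, and if pre-existing patterns count as events, the gain in power is about nil at persistence of 30% or less, about 1 to 5 points at 50%, and larger only above that. If only new-onset patterns count, it is about 0.5 to 1.6 points. The worst loss is about 0.3 point. Prevalence and persistence are assumptions throughout.

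The counting rule is a secondary clarification, conditional on what the Appendix says.

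**What to change.** 1. In section 4.0 .2, pre-specify that the four-group primary comparison is stratified on baseline tracing status (non-reassuring, not non-reassuring, unreadable) by a 3-df Cochran-Mantel-Haenszel test. Run the planned 10,000-sample Monte-Carlo exact test within strata. Keep all randomised women.
2. For this stratification, end the baseline reading at envelope opening and record that time. A window ending at CSE is partly post-randomisation, since assignment, apparently the oxytocin change, and the start of the bolus all come before the intrathecal injection.
3. Before any tracing is read, state in section 4.0 .2 whether a pattern already present at baseline counts as an event. If the Appendix has a rule, repeat it there.

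Cost: a few sentences, one time field, and a shifted window on a tracing already read off-line. Women with no tracing before envelope opening go in the unreadable stratum, which dilutes the gain. No extra patients or procedures are needed.

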There are many factors that contribute to alterations in the fetal heart rate including stage of labor, fetal head compression, cord compression, and uteroplacental insufficiency. Oxytocin is used in labor and delivery to increase the frequency of contractions and augment uterine contractile strength, thereby establishing a regular pattern of labor. However, the administration of exogenous oxytocin in the presence of an uncoordinated labor pattern confers a risk for increase in uterine contraction frequency, resulting in inadequate relaxation periods. This leads to an increase in the basal tone of the uterus, which may lead to a tetanic contraction with risk decreased uteroplacental blood flow and fetal hypoxemia (3). Since the introduction of oxytocin for labor induction in 1948, there have been multiple protocols for the administration of oxytocin, both for labor induction, as well as for augmentation of labor. Many institutions use an active management of labor protocol (AMOL) to facilitate labor and delivery through oxytocin management. Use of the AMOL protocol decreases the duration of labor and the Cesarean delivery rate for dystocia (4). The evidence is divided as to the effect of highversus low-dose oxytocin administration on fetal heart rate abnormalities (5-9). Merrill et al. randomized patients to low-versus high-dose oxytocin for augmentation or induction of labor (8). Oxytocin was decreased or discontinued more commonly in the high-dose group, both for uterine hyperstimulation and FHR abnormalities. In contrast, a study comparing high-dose oxytocin management with standard care found that there were no differences in fetal outcomes or the incidence of fetal distress between groups (9). One of the limitations of the previous studies is that the labor analgesia was not standardized;

and consisted of either traditional epidural (high dose) analgesia or intravenous opioids.

Labor analgesia itself has been implicated as a cause of non-reassuring fetal heart rate tracings. The combination of low-dose combined spinal epidural analgesia and the high-low-dose oxytocin have not been evaluated.

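### The unadjusted primary chi-square is valid, but it leaves out parity and the pre-CSE dilation and station already collected, at a modest cost in power

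*Combined protocol and SAP*

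**What the plan says.** All references are to the combined protocol and SAP.

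- **Endpoint and test (4.0 .2 Data evaluation).** "The primary endpoint is the incidence of non-reassuring fetal heart rate tracings during the first 60 minutes after the placement of CSE". The table is "constructed with the presence or absence of the endpoint as rows and the groups as" columns, and the groups are compared by a chi-square statistic with an exact p-value from 10,000 Monte-Carlo samples. No stratified, regression or other adjusted analysis is planned anywhere. Fetal station appears in this section only as one of the variables compared between groups.
- **Background (2.0).** The text speaks of "many factors that contribute to alterations in the fetal heart rate including stage of labor, fetal head compression", and goes on to cord compression and uteroplacental insufficiency.
- **Data collected (4.0 .1).** The form includes "cervical examination prior to placement of CSE (dilation, effacement, and station").
- **Randomisation (3.0, Protocol specific methods).** "Block randomization based on parity, via a computer generated random number table". The envelope is opened when the woman requests analgesia. The entry criteria set no limit on dilation or station.
- **Sample size (3.0 .2 Methods).** "Group sample sizes of 88 in each of the four groups achieves 80% power to detect a difference among the groups", by a 3-df chi-square at alpha 0.05. The assumed event rates are 8% and 23% with low oxytocin (with and without bolus), and 15% and 25% with high oxytocin.

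**The concern.** The plan records two baseline values that bear on factors it names itself as affecting the fetal heart rate, and it blocks the randomisation on a third. The primary test uses none of them. Parity is balanced by the blocks, but any outcome variation it explains stays in the error term. Dilation and station are balanced only by chance.

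If these values predict the endpoint, the primary comparison has less power than the same data could give, in a trial planned at 80%. There is also no pre-specified answer if the groups turn out to differ in labour progress. Comparing station between groups shows an imbalance but neither corrects for it nor adds precision.

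**Working it through.** **1. The plan's own figure.** The four stated rates are 15, 8, 25 and 23%, with mean p = 17.75%.

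- Deviations from the mean: −2.75, −9.75, 7.25 and 5.25 points. Mean square = (7.5625 + 95.0625 + 52.5625 + 27.5625)/4 = 45.69, or 0.004569 on the proportion scale.
- W² = 0.004569/(0.1775 × 0.8225) = 0.0313, so W = 0.177.
- Noncentrality = N·W² = 352 × 0.0313 = 11.0. Power of a 3-df chi-square at 0.05 is 80.4%; 80% needs N = 348.4, which is 88 per group.

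So 88 per group at 80% follows from the stated rates. The printed W of 0.19 would instead give 86.2% at 352, or 76 per group. That mismatch is a separate matter and does not affect this point.

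**2. Gain by approximation.** Let R² be the share of outcome variance explained by the baseline values. Adjustment multiplies the noncentrality by 1/(1 − R²) and the standard error of a standardised risk difference by √(1 − R²). R² is an assumption throughout.

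| Assumed R² | Power at N = 352 | SE ratio | Equivalent patients (R² × 352) |
|---|---|---|---|
| 0 | 80.4% | 1.000 | 0 |
| 2% | 81.3% | 0.990 | 7 |
| 5% | 82.6% | 0.975 | 18 |
| 10% | 84.8% | 0.949 | 35 |
| 15% | 87.0% | 0.922 | 53 |

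**3. Gain by simulation, one standardised covariate.** Each setting has 3,000 trials of 88 × 4, with intercepts set so that the marginal rates equal the plan's. Both tests are 3-df likelihood-ratio tests, so a change of test does not inflate the difference. The Monte-Carlo standard error of each power is about 0.6 points.

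| Assumed odds ratio per SD | Unadjusted | Adjusted | Gain (points) |
|---|---|---|---|
| 1.0 | 85.3% | 85.5% | 0.2 |
| 1.35 | 86.1% | 86.7% | 0.6 |
| 1.65 | 85.2% | 86.4% | 1.2 |
| 2.2 | 86.0% | 89.0% | 3.0 |
| 2.7 | 84.4% | 88.7% | 4.3 |

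A repeat run gave gains of 0.4, 0.8, 3.0 and 4.0 points at odds ratios 1.35 to 2.7. The 0.4 has a paired standard error of 0.27, so it is not distinguishable from zero.

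**4. Two independent covariates, same like-for-like comparison.**

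- Odds ratio 1.0 each: 85.5% vs 85.5%.
- 1.25 each (R² about 1.4%): 84.3% vs 85.4%, a gain of 1.1.
- 1.5 each (R² about 4.4%): 85.2% vs 87.1%, a gain of 1.9.
- 2.0 each (R² about 12%): 85.3% vs 89.7%, a gain of 4.4.

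The approximation in step 2 gives gains of 0.7, 2.0 and 5.1 points at those three R² values, so the two methods agree.

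**5. Why the simulated baselines exceed 80.4%.** Simulated Pearson chi-square power at the plan's rates was 82.4 to 83.9%, somewhat above the noncentral approximation. The likelihood-ratio test rejects slightly more often still: with covariates of no prognostic value the figures were 83.3% (Pearson) and 84.7% (adjusted likelihood-ratio). That difference of 1.4 points comes from the choice of test and should not be credited to adjustment.

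**6. Error rate and event count.** With no group effect, the chi-square rejected in 4.5 to 5.2% of trials. The adjusted test rejected in 5.1 to 5.3% in one set of runs and 4.8 to 5.6% in another. Expected events are 0.1775 × 352 = 62 overall and 0.08 × 88 = 7 in the smallest-rate arm.

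**The case against.** The best defence is that nothing here is an error. The unadjusted chi-square is valid under randomisation, it matches the test used for sizing, and its error rate already allows for chance imbalance. That stands in full. A reader might infer that leaving out dilation and station biases the result or inflates type I error. The design does not support that, and step 6 shows no inflation. In the worst-balanced 10% of null trials at an odds ratio of 2.0 for each of two covariates, the chi-square rejected 8.2% of the time against 4.8% adjusted (400 trials, standard error about 1.2 points). At 1.5 the figures were 8.2% and 7.0%, within noise. This is a statement about unlucky trials, not about the test's overall validity.

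A reader might also infer that the plan declares these values prognostic, so that precision is certainly being lost. That goes too far. The Background sentence is a general list, its order is not a ranking, and the endpoint is narrower: minimal or absent variability, late decelerations and persistent deceleration. Reading dilation and station as measures of labour stage and head compression is reasonable, but the documents do not say it. Gains of 3 points or more need an odds ratio of about 2.2 per SD or higher for a single covariate, and nothing in the documents supports or excludes that.

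Two practical objections also stand. First, the recorded examination precedes CSE but need not precede allocation: the envelope is opened at the request for analgesia, and oxytocin is changed then in two groups. Adjustment should use only values from before that moment. The same caution applies to the 30-minute pre-analgesia tracing, which might otherwise be a strong covariate. Second, moving from an exact Monte-Carlo test to a logistic model relies on large-sample theory with few events in one arm.

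**Conclusion.** The point holds as a modest inefficiency. The planned test is sound, but it leaves unused the randomisation factor and two baseline values that are already collected and plausibly related to the endpoint. The cost is about 0.5 to 4 points of power for an assumed odds ratio of 1.35 to 2.7 per SD, and about zero if the covariates are unrelated to the endpoint. In that last case the simulations show no loss from adjusting.

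The size rests on three assumptions: the strength of association, which the documents do not give; the plan's four event rates; and covariates treated as normally distributed. Parity's own contribution was not simulated separately. No conclusion of the trial becomes invalid if the plan is left as it is.

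**What to change.** In 4.0 .2 Data evaluation:

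- Make the primary four-group comparison a logistic model with group, parity, cervical dilation (cm) and station, with a 3-df test of group.
- Report risk differences between groups by standardisation over the whole sample. The conditional odds ratio can be given too, but its standard error does not itself shrink with adjustment.
- Use the last examination recorded before the envelope is opened. State a simple imputation for a missing value, for example the overall median taken without regard to group.
- Keep the planned chi-square with its Monte-Carlo exact p-value as a reported supporting result.

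The costs are small. Dilation, station and parity are already on the form, but 4.0 .1 lists no time for the examination or for envelope opening, so those times must be captured to apply the timing rule. The adjusted test is a large-sample one, with about 62 events overall and about 7 in the 8% arm. Sixty-two events are enough for three group terms and three covariates. A permutation p-value for the adjusted statistic, reshuffling groups within the parity blocks, would remove the reliance on large-sample theory. No extra patients or examinations are needed.

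### The only primary test is a 3-df comparison of four groups, so neither the fluid nor the oxytocin question is tested, and the oxytocin question has about 20% power rather than 80%

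*Combined protocol and SAP*

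**What the plan says.** Section 1.0 (Research Aims) poses two numbered questions. The first concerns fluid given before CSE. The second asks whether "there an association between the rate of oxytocin administration and non-reassuring" FHR changes are linked. The hypothesis is directional: it begins "Patients who receive a 1000 mL fluid bolus and lower rates of" oxytocin and predicts fewer non-reassuring changes.

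The group table in section 3.0 .2 (Methods) is a complete 2x2 factorial:

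| | Routine oxytocin | Half-dose oxytocin |
|---|---|---|
| 1000 mL bolus | A | B |
| No bolus | C | D |

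The sample-size paragraph in the same section states: "Group sample sizes of 88 in each of the four groups achieves 80% power". It ties this to one test, "using a 3 degrees of freedom Chi-Square Test with a significance level (alpha) of 0.05".

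Section 4.0 .2 (Data evaluation) cross-tabulates the endpoint by group and then says: "Differences in the frequency among groups will be assessed using a" chi-square statistic, with Monte-Carlo exact P values. Nothing else is specified for the primary endpoint. Post-hoc comparisons with a multiplicity correction are mentioned only for variables analysed by ANOVA or Kruskal-Wallis. The sentence on binomial and ordinal data falls under secondary outcomes and demographics and names no factor-level comparison.

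**The concern.** The analysis does not follow the design or the aims. A significant 3-df result says that the four proportions are not all equal. It is non-directional and does not identify which factor is responsible. Exact computation changes how the P value is obtained, not the hypothesis tested. A team following the plan to the letter could reach P < 0.05 and have no inferential answer to either question. Any factor claim would then rest on comparisons chosen after seeing the data.

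Two misreadings are likely. A significant omnibus result driven by fluid could be reported as support for lower oxytocin. A non-significant oxytocin comparison could be reported as no effect, although the trial was never sized to detect one.

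**Working it through.** **Inputs (section 3.0 .2, sample-size paragraph).** Assumed rates: A 15%, B 8%, C 25%, D 23%. There are 88 per group, N = 352, and alpha is 0.05 two-sided.

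**1. Reproduce the stated power.** The mean rate is p̄ = (0.15 + 0.08 + 0.25 + 0.23)/4 = 0.1775, so p̄(1 − p̄) = 0.14599. The mean squared deviation of the four rates is 0.004569.
- w = √(0.004569/0.14599) = 0.1769
- Noncentrality λ = 352 × 0.1769² = 11.02
- Noncentral chi-square, 3 df: power 80.4%. The smallest n per group that reaches 80% is 88.

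The stated 80% therefore reproduces from the rates. The noncentral chi-square is a large-sample approximation; direct simulation (200,000 trials) gives 83.5%. A side point to reconcile: the text also says "assuming an effect size (W) of 0.1900". That value gives 86.2% at 88 per group and needs only 76 per group for 80%. The argument below uses the rates and does not depend on W.

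**2. Where the omnibus signal comes from.** With equal groups the mean squared deviation splits exactly into three 1-df parts:

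| Part | Calculation | Value | Share |
|---|---|---|---|
| Fluid | ((0.24 − 0.115)/2)² | 0.003906 | 85.5% |
| Oxytocin | ((0.20 − 0.155)/2)² | 0.000506 | 11.1% |
| Interaction | ((0.15 − 0.08 − 0.25 + 0.23)/4)² | 0.000156 | 3.4% |

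**3. Power for each question.** This is the two-proportion test with n = 176 per factor level:

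power ≈ Φ{(|p₁ − p₂| − z√(2p̄(1 − p̄)/n)) / √((p₁(1 − p₁) + p₂(1 − p₂))/n)}

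With z = 1.96, the critical difference is 1.96 × √(2 × 0.14599/176) = 0.0798.
- Fluid, 11.5% vs 24.0%: (0.125 − 0.0798)/0.0402 = 1.12, power **87.0%**.
- Oxytocin, 15.5% vs 20.0%: (0.045 − 0.0798)/0.0407 = −0.86, power 19.6%, or **19.7%** counting both tails. If all 380 enrolled were evaluable (190 per level) it is about 21%.
- At alpha 0.025 each: fluid 79.9%, oxytocin about 13%.
- Oxytocin within the bolus groups (A vs B, 15% vs 8%, 88 each): 30.6%. Within the no-bolus groups (25% vs 23%): 5 to 6%.

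The 95% CI half-width for the oxytocin difference is 1.96 × √((0.20 × 0.80 + 0.155 × 0.845)/176) = 0.080, that is, 8 points around an assumed difference of 4.5 points. For 80% power the oxytocin contrast would need 1131 per level, 2262 in total.

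**4. How the omnibus test behaves if only one factor works (3 df, N = 352).**
- Only fluid (11.5%, 11.5%, 24%, 24%): omnibus power 73%, against 87% for the 1-df fluid test.
- Only oxytocin (20% vs 15.5%): omnibus power 13%.

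**5. Simulation at the protocol's rates (200,000 trials).** Fluid is significant in 87.5% of trials and oxytocin in 19.2%. Among trials with a significant omnibus test, oxytocin is significant in 22%.

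**6. Sensitivity to method.** A separate 100,000-trial simulation of the oxytocin main effect gave 19.2% pooled, 20.0% for Mantel-Haenszel stratified by fluid, and 24.7% for a logit-scale contrast. The interaction test had about 14% power.

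**The case against.** The strongest reply is that the protocol is internally consistent: it plans a 3-df test and powers that same test, and nowhere says that 80% applies to oxytocin alone. That is true, but the second research question is then left with no test and no power statement.

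A second reply is that the end of the Background and section 5.0 predict a benefit of the combination, which concerns group B, so a four-group comparison is a defensible first step. For B against C (8% vs 25%, 88 each) unadjusted power is 87%, and B vs C was significant in 95% of simulated omnibus-significant trials. This is a fair point about the design, but B vs C is not planned either, and it could not separate the two factors.

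Third, marginal contrasts average an assumed oxytocin effect of 7 points with bolus and 2 points without, and the interaction test is too weak to show whether pooling is safe. This stands as a limitation, and it is why the four cell rates should be reported beside the contrasts.

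Fourth, the planned cross-tabulation already shows direction descriptively. That is also correct, but a display is not a prespecified inference.

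**Conclusion.** The concern holds. The planned primary analysis gives no inferential answer to either research question, and the 80% describes only the omnibus test. At the protocol's own rates, power is about 87% for fluid and about 20% for oxytocin (19% to 25% by method; 31% for the most favourable oxytocin comparison tried, within the bolus groups).

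These figures rest on the assumed rates, equal groups of 88 and two-sided alpha 0.05. A larger true oxytocin effect would raise the 20%. The absence of any factor-level test does not depend on those assumptions. The omnibus test itself is valid; the fault is that it does not match the aims.

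**What to change.** Before unblinding, amend section 4.0 .2 and the sample-size paragraph as follows.

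- **Primary analysis:** a factorial analysis (logistic regression with both factors, or stratified Mantel-Haenszel) with two 1-df contrasts, bolus (A+B vs C+D) and oxytocin (B+D vs A+C). Report each as a risk difference with 95% CI.
- **Supporting results:** an interaction test, acknowledged as low-powered, with the four cell rates beside it. Keep the 3-df test as supportive. If a claim about the combination is wanted, name B vs C as a secondary comparison.
- **Multiplicity:** state a rule for the two primary tests, such as Bonferroni at 0.025 each.
- **Power:** replace the single statement with one per question (about 87% fluid, about 20% oxytocin at alpha 0.05), and say that a non-significant oxytocin result is inconclusive.

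The cost is wording only, with no extra patients or data. The downside is two primary tests instead of one: at 0.025 each, fluid keeps about 80% power and oxytocin falls to about 13%. The change makes the oxytocin question testable but not well powered; that would need about 2262 patients at the assumed rates.
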